2.3 Study Endpoints

The study endpoints are listed below, with greater detail concerning these endpoints provided in [Sections 2.3.2 to 2.3.10](#).

Primary Efficacy Endpoint

The primary efficacy endpoint is the change in WI-NRS from baseline to Week 6.

Key Secondary Efficacy Endpoints

The key secondary efficacy endpoints are as follows:

- WI-NRS 4-point responder rate at Week 6
- Change in ItchyQoL from baseline to Week 6

Additional Endpoints

Additional secondary efficacy endpoints include the following:

- WI-NRS 3-point responder rates
- Change in Average-Itch NRS (AI-NRS) and AI-NRS responder rates
- Change in 5-D Pruritus Scale
- Change in Static Patient Global Assessment of Itch Severity (sPGA)
- Change in Patient Global Impression of Change in Itch Severity (PGIC)
- Change in number of night-time scratching events per hour from baseline to Week 6

Safety endpoints include the following:

- Incidence of treatment-emergent adverse events (TEAEs) and serious adverse events (SAEs)
- Changes in clinical laboratory parameters following study drug exposure
- Changes in vital sign and electrocardiogram (ECG) parameters following study drug exposure
- Plasma concentrations of serlopitant and metabolites

Exploratory endpoints include the following:

- Change in Investigators' Global Assessment of atopic dermatitis severity (IGA-AD)
- Change in sleep efficiency
- Change in mean activity during the sleep period

2.3.1 *Endpoint Data Capture*

The study endpoints will be captured within five electronic systems, the electronic data capture (eDC system) , subject eDiary, subject actigraphy devices, central laboratories (ACM Global) and centralized ECG assessments. The adverse events, vital signs, and IGA-AD will be captured in the CRF. The eDiary will capture the WI-NRS, ItchyQoL, AI-NRS, sPGA, and PGIC. The actigraphy devices will record night-time scratching, sleep efficiency, and mean activity during the sleep period during each night the subjects is on study.

2.3.2 *Itch Numeric Rating Scale*

The Itch NRS is an instrument for measurement of itch intensity that asks subjects to rate the intensity of their itch on an 11-point scale ranging from 0 (no itch) to 10 (worst itch imaginable) during a 24-hour recall period. Both WI-NRS and AI-NRS during a 24-hour recall period will be captured. The daily NRS results will be summarized at Weeks 2, 4, 6 and follow-up as outlined in [Section 2.4](#). A 4-point responder is a subject who had at least a 4-point reduction in score between the visit and baseline. A 3-point responder is similarly defined.

2.3.3 *Static Patient Global Assessment of Itch Severity*

The sPGA assesses overall itch severity by asking the severity of itchiness in the past 7 days on a 5-point scale as none (0), mild (1), moderate (2), severe (3), and very severe (4).

2.3.4 *Patient Global Impression of Change in Itch Severity*

The PGIC in Itch Severity is a single item measure that assesses the change in overall itch severity since the Baseline visit on a 7-point scale from (very much better) to (very much worse).

2.3.5 *ItchyQoL*

ItchyQoL is a 22-item pruritus-specific instrument that measures the degree to which pruritus affects quality-of-life. The responses to the items are Never (1), Rarely (2), Sometimes (3), Often (4) and All the Time (5). This impact is quantified into 3 subscales (symptom, function, emotion) and an overall score. A higher score corresponds to a more adverse impact. The overall score is the average of the 22 items. If an item is missing the total score will be missing. The score for each subscale is the average score for the items that make up the subscale. The items that make up the subscales are,

- Symptom subscale score (items 1-6):
 - My itchy skin condition bleeds,
 - My skin hurts because of my itchy skin condition,
 - My itchy skin condition burns or stings,
 - I get scars from my itchy skin condition,

- I need to scratch my itchy skin condition,
- Temperature/seasonal changes aggravate my itchy skin condition
- Function subscale score (items 7-13):
 - I spend a lot of money treating my itchy skin condition,
 - My itchy skin condition makes it hard to work or do what I enjoy,
 - My itchy skin condition affects my interaction with others,
 - My itchy skin condition affects how well I sleep,
 - My itchy skin often makes it difficult to concentrate,
 - My itchy skin condition limits the types of clothes I can wear,
 - My itchy skin condition forces me to buy special soaps, detergents, and lotions.
- Emotion subscale score (items 14-22):
 - I am frustrated by my itchy skin condition,
 - I am embarrassed by my itchy skin condition,
 - My itchy skin condition drives me crazy/nuts,
 - My itchy skin condition makes me feel angry or irritable,
 - My itchy skin condition makes me feel depressed or sad,
 - I worry about what other people think about me because of my itchy skin condition,
 - I worry that the itching will last forever,
 - I feel self-conscious because of my itchy skin condition,
 - My personality has changed because of my itchy skin condition.

2.3.6 5-D Pruritus Scale

The 5-D Pruritus Scale assesses the five domains of degree, duration, direction, disability and distribution of pruritus. Subjects rate their symptoms over the preceding 2-week period. The scores of each of the five domains are achieved separately and then summed together to obtain a total 5-D score (Elman 2010) resulting in a range of scores from 5 to 25 (no to most severe pruritus). If any one item is missing the total score will be missing.

The single-item domains, duration, degree and direction, are captured on a likert scale. The score for these domains is equal to the value recorded for the domain (i.e. 1 to 5). The disability domain includes four items that assess the impact of itching on: sleep, leisure /social activities, housework/errands and work/school. The score for the disability domain is achieved by taking the highest score on any of the four items. For the distribution domain, the number of affected body parts is given a point total (0–2 = 1, 3–5 = 2, 6–10 = 3, 11–13 = 4, 14–16 = 5).

2.3.7 Actigraphy

The actigraphy assessments requires each subject to wear the actigraphy devices, which are the size of a medium size wrist watch, on each wrist at night (during sleep), with the option to wear them during the waking hours as well. The waking hours data will be captured but not directly analyzed. The devices are returned to the study site where the data are downloaded and sent for analysis. Subjects will be permitted to not wear the devices up to three nights over any seven-day period (i.e. up to three nights per week).

The 3-dimensional acceleration data (m/sec^2) from the actigraphy device is analyzed to discriminate scratching from other nighttime events. These scratching results will include

1. Scratching Endpoints

- a. scratching time per sleep period (the time of the first and last itching event),
- b. number of scratching events per sleep period
- c. the itching events per hour (*secondary endpoints*) and
- d. the intensity of itching per hours (seconds of itching per hour).

2. Sleep Endpoints

- a. sleep duration (end of sleep – start of sleep),
- b. total sleep time (time subject was asleep during sleep period, does not include wake time during sleep period),
- c. sleep efficiency (*exploratory endpoint*: sleep time/sleep duration),
- d. Wake After Sleep Onset (WASO) and
- e. the mean activity during the sleep period (*exploratory endpoint*).

For the actigraphy endpoints to mirror the techniques used in development of the actigraphy tool as outlined in Moreau et al. (2017), the analysis will be limited to sleep periods between 30 minutes and 18 hours in length.

2.3.8 Investigators' Global Assessment of Atopic Dermatitis Severity

The IGA-AD is an instrument used to assess the overall severity of atopic dermatitis at a given time point, as determined by the investigator. It consists of a 6-point scale ranging from 0 (clear) to 5 (very severe). An IGA-AD responder is defined as a subject with a score of “clear” or “almost clear” and at least a 2-grade reduction from baseline score.

2.3.9 Safety Parameters

Vital signs will include measurements of heart rate, sitting blood pressure, respiration rate, and temperature. A standard 12-lead ECG will be performed and centrally read. From this central read the following parameters will be available: RR, PR, QRS, QT, HR, QTcB, QTcF, and the “interpretation” (Normal or Abnormal). If the result is considered abnormal, the specific findings will also be provided. Physical examination abnormalities identified as preexisting before treatment will be recorded as medical history. Laboratory results identified as clinically significant and abnormal before treatment will be recorded as medical history or associated with an ongoing historical event. Clinically significant new or worsened abnormalities that appear after treatment will be recorded as AEs.

Vital signs, ECG parameters and relevant interpretations, and laboratory results will be listed.

2.3.10 Pharmacokinetic Measurements

Blood samples for pharmacokinetic (PK) measurements will be collected as outlined in [Table 2](#).

2.4 Study Day and Visit Windows

Summary tables will report data based upon the protocol scheduled time points (Weeks 2, 4, 6 and Follow-up). Assessment will be assigned to these time points based upon the study day they are performed on. The derivation of study day depends upon whether the event occurred prior to or after treatment. This results in the first day of treatment being on day 1 and the day prior to the first day of treatment being day -1. For events that occur prior to the first day of treatment the following definition is used,

$$\text{Study day} = \text{date of assessment} - \text{date of first treatment}.$$

For events that occur on or after the first day of treatment, a plus one is added,

$$\text{Study day} = \text{date of assessment} - \text{date of first treatment} + 1.$$

The analysis windows used to report non-daily endpoints as well as ItchyQoL, sPGA and PGIC are outlined in [Table 3](#). If more than one assessment is available within the range the assessment closest to the target day is reported for the analyses window. If two observations exist with the same distance to the target day, the first observation is used.

Table 3 Analysis Windows

Visit	Range	Target Day
Baseline	Day \leq 1	Day 1
Week 2	Day 2 to Day 21	Day 15
Week 4	Day 22 to Day 35	Day 29
Week 6	Day 36 to Day 57	Day 43
Week 10	> Day 57	Day 71

In addition to the analysis windows, data will be summarized at Follow-Up. The Follow-Up assessment will be the last assessment available that is at least seven days after the end of treatment. Should no post treatment assessments be available the subject will not have a follow-up assessment. While a Week 10 analysis window is defined, data tables will be limited to Baseline, Week 2, 4, 6 and Follow-up.

eDiary and actigraphy daily results (WI-NRS, AI-NRS, night-time scratching, sleep efficiency and mean activity during the sleep) will be summarized at Baseline, Week 2, 4, 6 and Follow-up. The seven days leading up to the time point (see [Table 4](#) range), will be used to create the summary measures unless the subject does not have at least seven results. In this case as many observations as are available within the complete data range will be used and additional data from the extended range (see [Table 4](#)) will be used until seven data points are achieved or the end of the extended range is reached. An example of this algorithm can be found in [Section 3.4.1](#).

Table 4 Daily Windows

Visit	Range (complete data)	Extended Range
Baseline	Day -7 to -1	Day -11 to -8
Week 2	Day 8 to Day 14	Day 15 to Day 18
Week 4	Day 22 to Day 28	Day 29 to Day 32
Week 6	Day 36 to Day 42	Day 43 to Day 46

An additional ‘Follow-Up’ timepoint will also be created. This timepoint includes the last 7 post treatment observations that are at least 7 days after the end of treatment.

For the WI-NRS and AI-NRS endpoints results from within the windows provided in [Table 4](#) and at Follow-up may not be used based upon the confounding logic outlined in [Section 2.6](#).

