The Week 4 visit occurs 28 days (\pm 3 days) after the Baseline visit (Study Day 26-32). At the Week 4 visit, the following procedures and assessments are to be performed:

- Vital signs
- IGA-AD
- 5-D Pruritus Scale
- PK blood sample collection
- Concomitant medications
- AEs
- Collect returned study drug
- Dispense study drug

6.5.7 *Week 6 Visit*

The Week 6 visit occurs 42 days (\pm 3 days) after the Baseline visit (Study Day 40-46). At this visit, the following procedures and assessments are to be performed:

- Vital signs (including weight)
- Targeted physical examination
- Laboratory
 - Reproductive endocrine labs for females
 - Urine pregnancy test for females of childbearing potential (with positive or equivocal results confirmed by a serum pregnancy test)

- Endocrine and cardiac
- Hematology
- Chemistry
- Urinalysis
- IGA-AD
- 5-D Pruritus Scale
- PK blood sample collection
- Concomitant medications
- AEs
- Collect returned study drug

6.5.8 *Early Treatment Discontinuation Visit*

The ETD visit occurs within 7 days of the last dose of study drug for subjects who discontinue study drug treatment early. At this visit, the following procedures and assessments are to be performed:

- Vital signs (including weight)
- Targeted physical examination
- Laboratory
 - Reproductive endocrine labs for females
 - Urine pregnancy test for females of childbearing potential (with positive or equivocal results confirmed by a serum pregnancy test)
 - Endocrine and cardiac
 - Hematology
 - Chemistry
 - Urinalysis
- IGA-AD
- 5-D Pruritus Scale
- PK blood sample collection
- Concomitant medications
- AEs
- Collect returned study drug

6.5.9 *Follow-up Visit*

The Follow-up visit occurs 28 days (\pm 3 days) after the Week 6 visit (Study Day 68-74) or the ETD visit (for subjects who discontinue study drug early). Subjects who discontinue study drug prior to Study Day 15 should have a follow-up visit 6 weeks (\pm 3 days) after randomization (Study Day 40-46) so that all randomized subjects will have a Week 6 evaluation. At the Follow-up visit, the following procedures and assessments are to be performed:

- Vital signs (including weight)
- Targeted physical examination
- ECG
- Laboratory
 - Reproductive endocrine labs for females
 - Urine pregnancy test for females of childbearing potential (with positive or equivocal results confirmed by a serum pregnancy test)
 - Endocrine and cardiac
 - Hematology
 - Chemistry
 - Urinalysis
- IGA-AD
- 5-D Pruritus Scale

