3.5.2 Clinical Laboratory Evaluations

Summary statistics for actual values and for changes from baseline will be tabulated for clinical laboratory results by analysis window. Shifts from baseline clinical laboratory values based upon the normal range will be tabulated. These tables will utilize the normal ranges provided for the individual sample.

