3.5.4 Electrocardiogram Results

The overall ECG assessment (abnormal or normal) will be summarized by treatment and analysis window. The QTcF values will be summarized by treatment and analysis window as both the QTcF value and change from baseline. A summary of the number of subjects with a value > 450, 480 and 500 and the numbers of subjects with change from baseline values > 30 and 60 by treatment and analysis window will be produced.

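### SAP Table 3 places off-drug follow-up visits of early stoppers in the Week 6 safety rows, and any Week 6 QTcF row would hold essentially nothing else

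*SAP*

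**What the plan says.** **Windowing rule.** SAP 2.4 assigns non-daily assessments to time points by study day. The Week 6 range in Table 3 is "Day 36 to Day 57", with target Day 43. Ties are handled by proximity: "If more than one assessment is available within the range the assessment closest to the target day is reported for the analyses window". Time since the last dose plays no part.

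**Follow-up row.** This row is an addition: "In addition to the analysis windows, data will be summarized at Follow-Up". It is defined as follows: "The Follow-Up assessment will be the last assessment available that is at least seven days after the end of treatment". Nothing removes such an assessment from its Table 3 window. On which rows appear, the SAP says that "data tables will be limited to Baseline, Week 2, 4, 6 and Follow-up".

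**Safety tables.** SAP 3.5.2 has laboratory summaries "tabulated for clinical laboratory results by analysis window". SAP 3.5.4 says: "The QTcF values will be summarized by treatment and analysis window as both the QTcF value and change from baseline"; it also counts values above 450, 480 and 500 and changes above 30 and 60 by window. SAP 3.5.3 summarises vital signs by measurement day, so Table 3 reaches them only through the general rule in SAP 2.4.

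**Visit calendar.** Protocol 6.5.9 and Protocol Table 2 put follow-up 28 days (±3) after the Week 6 visit or the early treatment discontinuation (ETD) visit. Subjects who stop before Day 15 instead have it on Day 40-46, "so that all randomized subjects will have a Week 6 evaluation". That visit includes laboratory tests, vital signs and ECG. Both schedules (Protocol Table 2, SAP Table 2) list ECG at Screening, Week 2 and Follow-up only, with none at Week 4, Week 6 or ETD.

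**The concern.** Safety and tolerability of repeated doses is a stated secondary objective. A reader of a table by treatment group will take a row labelled Week 6 as the end-of-treatment picture. If part of that row comes from subjects who stopped weeks earlier and have cleared the drug, an on-drug shift in a laboratory parameter is averaged with values that cannot show it.

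The QTcF table is the sharper case. No ECG is planned at the end of treatment, yet the windowing rule can generate a Week 6 row. That row would look like steady-state QTcF by dose and would contain almost no on-drug data. In both tables one follow-up value can be counted under Week 6 and again under Follow-up.

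**Working it through.** **1. Reproduce the protocol's own days.** Completers' follow-up: 43 + 28 ± 3 = Day 68-74. Stops before Day 15: 1 + 42 ± 3 = Day 40-46. Both match Protocol 6.5.9. Completers' follow-up stays outside Day 36-57 even at the extremes (40 + 25 = Day 65; 46 + 31 = Day 77).

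**2. Which early stoppers enter the Week 6 window.** Let L be the last-dose day and e the lag to the ETD visit (0 to 7 days).
- L < 15: follow-up is on Day 40-46, always inside Day 36-57.
- L ≥ 15: follow-up is on day L + e + 28 ± 3. It is always inside if L + 7 + 28 + 3 ≤ 57, so L ≤ 19. It can be inside if L + 0 + 28 − 3 ≤ 57, so L ≤ 32.
- SAP 1.3 words the timing differently: 4 weeks after end of treatment, or Week 6 if later. Then it is always inside for L ≤ 26 and possibly inside up to L = 32.

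**3. Which value is selected.** All combinations of L = 1 to 42, e = 0 to 7 and visit deviation −3 to +3 were enumerated. Whenever follow-up falls in Day 36-57, it is the laboratory value closest to Day 43 in 1428 of 1428 combinations under the protocol timing and in 1604 of 1624 under the SAP timing. In the other 20 the ETD value is selected.

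**4. Is an on-drug value pushed out?** Under the protocol timing, a later stopper's follow-up by Day 57 needs an ETD visit by 57 − 25 = Day 32. A subject who stops before Day 15 has the ETD visit by 14 + 7 = Day 21. These visits belong to the Week 2 (Day 2-21) or Week 4 (Day 22-35) window. Under the SAP timing, an ETD visit that does reach the Week 6 window is the value selected. So no on-drug Week 6 value is lost.

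**5. Time off drug.** Nominal: 43 − 1 = 42 days for the earliest stop, and 28 days for a later stopper with e = 0. With visit windows: 46 − 1 = 45 down to 28 − 3 = 25 days. The fraction remaining is 0.5^(24 × days / half-life), with the half-life of 70-80 h from Protocol 1.3.1:

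| Days off drug | 70 h | 80 h |
|---|---|---|
| 25 | 0.26% | 0.55% |
| 28 | 0.13% | 0.30% |
| 42 | 0.005% | 0.016% |
| 45 | 0.002% | 0.009% |

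**6. ECG.** A completer has no scheduled ECG between the Week 2 visit (Day 13-17) and follow-up (Day 68-74). The only scheduled ECGs that can fall in Day 36-57 are those in step 2. This does not depend on how many subjects stop. Protocol 6.2.4 allows unscheduled ECGs when clinically indicated; only these could add an on-drug value.

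**7. Size in the laboratory row (assumptions).** The documents give no discontinuation rate. Assume that last-dose days are uniform over Days 1-41, that timing is nominal and that every discontinuer attends follow-up.
- e = 0: follow-up is in the window for L ≤ 29, so 29/41 = 70.7%.
- e = 7: L ≤ 22, so 22/41 = 53.7%.
- e uniform over 0-7: 62.2%.
- If 10% of 450 discontinue (45 subjects): 0.537 × 45 ≈ 24. If 20% (90 subjects): 0.707 × 90 ≈ 64.
- With equal rates by arm, two thirds are on active drug: about 16 to 42.

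**The case against.** **The Week 6 QTcF row is inferred.** SAP 2.4 ties the tables to the scheduled time points, and its list of rows can be read as a ceiling. A programmer might produce no Week 6 ECG row, and if one appeared its small n would be visible. This is fair, and it is why the point is worded as any such row. But tabulation by analysis window permits the row, and nothing suppresses it.

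**An off-drug Week 6 evaluation is deliberate.** The protocol says so for stops before Day 15. That serves an intention-to-treat reading of efficacy, and the efficacy windows need no change. It does not say that safety rows should mix on-drug and off-drug values, and it does not cover later stoppers.

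**Other provisions limit the harm.** These tables are descriptive. Adverse events are counted independently of Table 3, clinically significant new abnormalities become adverse events, individual results are listed, and an independent committee reviews unblinded safety data. All of this stands. It limits the consequence but does not correct the tables.

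**Stronger readings that a reader might infer.** One is that washed-out values replace on-drug Week 6 values. They do not (step 4): without the follow-up value the cell would be empty. Another is that 24 to 64 exposed subjects dilute the laboratory row. That count pools placebo, for whom washout means nothing, and assumes full attendance at follow-up, so it is an upper figure under assumed rates. A third is that vital signs are affected just as explicitly as laboratory values. SAP 3.5.3 does not say so.

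**Conclusion.** The point holds in this form. Because Table 3 has no on-treatment condition, the Week 6 laboratory row, and the vital-sign row if Table 3 is applied to it, mixes on-drug completers with early stoppers nominally 28 to 42 days off drug. One value can appear under both Week 6 and Follow-up. Any Week 6 QTcF row would consist of off-drug follow-up ECGs apart from unscheduled ones; this follows from the schedules and needs no assumption.

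The extent of mixing in the laboratory row is not known. The figures of at most about 24 to 64 subjects, or 16 to 42 on active drug, rest on an assumed 10-20% discontinuation rate, uniform stop days, full attendance and, for the active-drug figure, equal rates by arm. At lower rates the effect could be trivial. The documents do not support a claim that on-drug Week 6 data are lost or that a safety signal would be hidden altogether. The primary analysis uses the daily windows of SAP Table 4 and is unaffected.

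**What to change.** In SAP 2.4, for laboratory, vital-sign and ECG summaries only:

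- Admit an assessment to Week 2, 4 or 6 only if it was made no more than 7 days after the last dose. A cut at less than 7 days would be wrong. The protocol allows the ETD visit up to 7 days after the last dose, and because the Follow-up row keeps only the last assessment, a day-7 ETD value would then appear in no row for subjects who attend follow-up.
- Report later assessments only at Follow-up, defined for these tables as more than 7 days after the last dose.
- Limit the scheduled ECG and QTcF tables to Baseline, Week 2 and Follow-up.
- State in SAP 3.5.3 whether vital signs follow Table 3.

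Leave the efficacy windows as they are. Narrowing the Week 6 window to Day 40-46 would not help, because follow-up visits after a last dose on Day 1 to 21 can still fall there. The follow-up timing in Protocol 6.5.9 and SAP 1.3 should also be reconciled.

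The cost is a few lines of SAP text and one programming condition, with no new data. The Week 6 safety rows lose some early discontinuers, who remain in the Follow-up row.
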